#### CONTRAINDICATIONS

17. Patient has a history of sensitivity to any of the study medications, medications used in the study (including anesthesia), or their components or a history of drug or other allergy that, in the opinion of the investigator or Medical Monitor, contraindicates their participation
18. Patient has any medical condition that may put them at increased risk with exposure to GSK1358820 including diagnosed myasthenia gravis, Eaton-Lambert syndrome, or amyotrophic lateral sclerosis
19. Females who are pregnant, nursing or planning a pregnancy during the study

#### DIAGNOSTIC ASSESSMENTS AND OTHER CRITERIA

20. Patient has a post void residual volume above 200 mLf for patients who micturate or have a mixed catheterization/spontaneous micturition pattern.
21. Patient has a 24-hour total volume of urine voided >3000 mL of urine collected over 24 consecutive hours during the 3-day bladder diary collection period in the Screening phase
22. Patient is currently participating in or has previously participated in another therapeutic study within 30 days prior to the start of the Screening phase
23. Patient has any condition or situation which, in the investigator's (or subinvestigator's) opinion, puts the patient at significant risk, may confound the study results, or may interfere significantly with the patient's participation in the study

f: The PVR measurement can be repeated once; the patient is to be excluded if the repeated measure is above 200 mL

### 5.3. Re-treatment Criteria

Patient can request re-treatment at any time the scheduled post-treatment since week 12 after treatment. The following re-treatment criteria must be used for the qualification of patient. As well the patient can requests re-treatment via telephone. If the patient requests re-treatment via telephone, a qualification for re-treatment visit should be conducted within approximately 1-2 weeks of the patient request.

#### Qualification for re-treatment criteria:

- 1) Patient must have initiated request for re-treatment

- 2) Patient experienced  $\geq 4$  episodes of urinary incontinence, with no more than one incontinence-free day, as determined by the 3-day patient bladder diary completed in the week prior to the Qualification for Treatment visit
- 3) PVR urine volume is  $< 200$  mL (for patients who micturate or have a mixed catheterization/spontaneous micturition pattern)
- 4) Body weight  $\geq 40$  kg
- 5) Investigator deemed re-treatment appropriate and no condition or situation existed which, in the investigator's opinion (or sub-investigator's opinion), put the patient at significant risk from receiving a repeat treatment

Once these criteria are met, the patient who qualifies should be treated within 21 days of qualification, provided that all the following re-treatment criteria are met on the day of re-treatment.

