
 
• To evaluate the safety of a single dose treatment of GSK1358820 200 U compared with placebo
 
• To evaluate the safety of a repeated dose treatment of GSK1358820 200 U
 
	
 
• Adverse events
 
• Safety parameter 
 
• Vital signs and physical examination
 
• Clinical laboratory (hematology, blood chemistry and urinalysis)
 
• Urine culture and sensitivity
 
• Post void residual (PVR) urine volume
 
• Use of clean intermittent catheterization (CIC) for urinary retention / elevated PVR [Only patients who are able to spontaneously void (excluding mixed catheterization) at baseline]
 
• Kidney and bladder ultrasound
 
• Pregnancy test
 
• Twelve-lead electrocardiogram (ECG)
 
 
 

Other	

 
• To evaluate the existence of toxin-neutralizing antibody after the treatment of GSK1358820 200U
 
	
 
• Neutralizing antibody measurement
 

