**Day of re-treatment criteria:**

- 1) Patient is asymptomatic for UTI on day of treatment.
- 2) Patient had discontinued any antiplatelet or anticoagulant therapy or medications with anticoagulative effects 3 days prior to re-treatment. Some medications may need to have been withheld for  $> 3$  days per clinical judgment of the investigator (or sub-investigator)
- 3) Negative urine pregnancy test for women of childbearing potential.
- 4) For patients without a UTI as determined from the urinalysis or urine culture using the sample collected at qualification for re-treatment visit and/or investigator opinion, has initiated prophylactic antibiotic medication 1 to 3 days prior to study treatment. For patients with a UTI as determined from the urinalysis or urine culture and/or investigator opinion, has initiated antibiotic medication at least 5 days prior to study treatment.
- 5) No occurrence of bladder stones since entry into the study
- 6) A minimum of 12 weeks (84 days) must have elapsed since the previous treatment
- 7) Period after 1st treatment did not exceed 36 weeks
- 8) Investigator (or sub-investigator) continued to deem a repeat treatment was appropriate and no condition or situation existed which in the investigator's opinion put the patient at significant risk from receiving a repeat treatment

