4. ANALYSIS POPULATIONS

Population	Definition / Criteria	Analyses Evaluated
Screened	
 Comprise all screened subjects 	
 Study Population
Enrolled	
 All participants who passed screening and entered the study. Included are: only Randomized Participants Note screening failures (who never passed screening even if rescreened) are excluded from the Enrolled population as they did not enter the study. 	
 Study Population
Full Analysis Set 1 (FAS1)	
 Comprise all randomized subjects who have at least 1 post-baseline efficacy assessment. This population will be based on the treatment to which the subject was randomized (this will be applied to FAS2 and FAS3). Any subject who receives a treatment randomization number will be considered to have been randomized. 	
 Study Population Efficacy for the TC 1 (double blind phase)
Full Analysis Set 2 (FAS2)	
 Comprise all randomized subjects who have at least 1 post-2nd treatment efficacy assessment after 2nd treatment. 	
 Efficacy for the TC 2
Full Analysis Set 3 (FAS3)	
 Comprise all randomized subjects who have at least 1 post-3rd treatment efficacy assessment after 3rd treatment. 	
 Efficacy for the TC 3
Safety for double blind phase (SPDB)	
 Comprise all subjects who receive at least one dose of study treatment. This population will be based on the treatment the subject actually received (this will be applied to all safety population). 	
 Safety for the TC 1 (double blind phase)
Safety 1 (SP1)	
 Comprise all subjects who receive at least one dose of GSK1358820 	
 Safety for at least one dose of GSK1358820 treatment
Safety 2 (SP2)	
 Comprise all subjects who receive at least two doses of GSK1358820 	
 Safety for two doses of GSK1358820 treatment
Safety 3 (SP3)	
 Comprise all subjects who receive three doses of GSK1358820. 	
 Safety for three doses of GSK1358820

Population	Definition / Criteria	Analyses Evaluated
		treatment

NOTES :

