3.45.	SP1	AE1	Summary of All Adverse Events Overall Period	ICH E3	Y	Y
3.46.	SP1	AE1	Summary of All Treatment-Related Adverse Events Overall Period	GSK CTR	Y	Y
3.47.	SP1	AE1	Summary of All Study Drug-Related Adverse Events Overall Period	GSK CTR	Y	Y

CONFIDENTIAL

204948

Safety : Tables						
No.	Population	IDSL / TST ID / Example Shell	Title	Programming Notes	Report at Interim	Report at Final
3.48.	SP1	AE1	Summary of All Injection Procedure-Related Adverse Events Overall Period	GSK CTR	Y	Y
3.49.	SP1	AE5A	Summary of All Adverse Events by maximum severity: Overall Period	ICH E3	Y	Y
3.50.	SP1	AE5A	Summary of All Treatment-Related Adverse Events by maximum severity: Overall Period	GSK CTR	Y	Y
3.51.	SP1	AE5A	Summary of All Study Drug-Related Adverse Events by maximum severity: Overall Period	GSK CTR	Y	Y
3.52.	SP1	AE5A	Summary of All Injection Procedure-Related Adverse Events by maximum severity: Overall Period	GSK CTR	Y	Y
Serious and Other Significant Adverse Events						
3.53.	SPDB	AE1	Summary of Serious Adverse Events TC1 <= 84 days from the first treatment	IDSL / GSK CTR	Y	
3.54.	SPDB	AE1	Summary of Special Interest Adverse Events TC1 <= 84 days from the first treatment		Y	
3.55.	SPDB	AE1	Summary of Serious Adverse Events TC1	IDSL / GSK CTR	Y	Y
3.56.	SPDB	AE16	Summary of Serious Adverse Events by System Organ Class and Preferred Term (Number of Participants and Occurrences) TC1	FDAAA, EudraCT	Y	Y
3.57.	SPDB	AE1	Summary of Special Interest Adverse Events TC1		Y	Y
3.58.	SP1	AE1	Summary of Serious Adverse Events: GTC1	IDSL / GSK CTR		Y
3.59.	SP1	AE16	Summary of Serious Adverse Events by System Organ Class and Preferred Term (Number of Participants and Occurrences): GTC1	FDAAA, EudraCT		Y

CONFIDENTIAL

204948

Safety : Tables						
No.	Population	IDSL / TST ID / Example Shell	Title	Programming Notes	Report at Interim	Report at Final
3.60.	SP1	AE1	Summary of Special Interest Adverse Events: GTC1			Y
3.61.	SP2	AE1	Summary of Serious Adverse Events: GTC2	IDSL / GSK CTR		Y
3.62.	SP2	AE16	Summary of Serious Adverse Events by System Organ Class and Preferred Term (Number of Participants and Occurrences): GTC2	FDAAA, EudraCT		Y
3.63.	SP2	AE1	Summary of Special Interest Adverse Events: GTC2			Y
3.64.	SP3	AE1	Summary of Serious Adverse Events: GTC3	IDSL / GSK CTR		Y
3.65.	SP3	AE16	Summary of Serious Adverse Events by System Organ Class and Preferred Term (Number of Participants and Occurrences): GTC3	FDAAA, EudraCT		Y

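### Differences between the planned treatment-cycle tables can reflect who was re-treated and how long each cycle lasted, rather than the effect of repeated dosing

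*Protocol*

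**What the plan says.** Protocol 5.3 lists the conditions for re-treatment. "Patient must have initiated request for re-treatment" comes first. Incontinence must have returned (at least 4 episodes in the 3-day diary), and PVR must be below 200 mL "for patients who micturate or have a mixed catheterization/spontaneous micturition pattern". The investigator must judge re-treatment appropriate, with no condition that "put the patient at significant risk from receiving a repeat treatment". That judgement is repeated on the day of re-treatment. The subject must then also be free of UTI symptoms, have had no bladder stones since entry, be at least 84 days past the last treatment, and meet the time limit: "Period after 1st treatment did not exceed 36 weeks".

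SAP 4 and SAP 8 assign a separate population to the AEs of each active cycle. SP1 has at least one active dose (GTC1). The SP2 definition reads "Comprise all subjects who receive at least two doses of GSK1358820" (GTC2). SP3 has three active doses (GTC3). The cycle tables that carry urinary retention are Table 3.60, "Summary of Special Interest Adverse Events: GTC1", on SP1; Table 3.63, "Summary of Special Interest Adverse Events: GTC2", on SP2; and Table 3.66 on SP3. Efficacy moves from FAS1 to FAS2 to FAS3, with change always taken from study baseline (SAP 5.2). Protocol 9.3.1 sets the same nesting.

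The AE window of 84 days or less is planned for TC1 only (SAP 8.1 and 11.4.1.2). One stated safety objective is "To evaluate the safety of a repeated dose treatment of GSK1358820 200 U".

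**The concern.** The cycle tables are the main aggregate evidence on repeated dosing, and a reader will look from one cycle to the next. Three features stand in the way of that reading.

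- **Selection on safety.** A subject who had retention or raised residual urine after one injection may be less likely to receive the next, and then drops out of the later table.
- **Selection on efficacy.** FAS2 and FAS3 hold only subjects whose incontinence came back in time for re-treatment by Week 36. Subjects with a lasting response are absent, so a FAS2 mean cannot be set beside the FAS1 mean.
- **Unequal time at risk.** The cycle AE tables give the number and percentage of subjects with an event over cycles of very different length.

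No planned table gives earlier-cycle results restricted to the subjects who went on, and no caution about reading across cycles was found. The risk is unwarranted reassurance about repeat injections, or a misread efficacy trend.

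**Working it through.** The plan states no cycle-specific rate, so there is no figure of its own to reproduce on this point.

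**1. Time at risk** (Protocol 4.2 and 5.3; study exit at Week 48)
- GTC1, active-first: 48 weeks if never re-treated, 12 if re-treated at the earliest date.
- Second injection, Week 12 to 36: at most 48 − 12 = 36 weeks remain, at least 48 − 36 = 12.
- Third injection, earliest Week 12 + 12 = 24, latest Week 36: 48 − 24 = 24 down to 48 − 36 = 12 weeks remain.

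The longest GTC1 is therefore 48/12 = 4 times the shortest GTC3. Because 36 + 12 = 48, every active cycle has nominally 84 days of follow-up unless the subject withdraws; the ±7-day window at Week 48 can shift this slightly.

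**2. Selection and retention**

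Inputs:
- m = 0.172, the first-treatment retention rate on 200 U in the earlier studies (Protocol 4.6.1).
- rho, the within-subject correlation of retention across doses: not in the documents, an assumption.
- r, the chance of re-treatment after a retention event relative to no event: not in the documents, taken from 0 to 1.

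Each subject's risk is held constant from dose to dose, so there is no true change. Let E = m² + rho·m(1 − m) and W = r·m + 1 − m. Then:
- GTC2 rate in SP2 = (r·E + m − E)/W
- GTC1 rate in the same SP2 subjects = r·m/W

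At r = 0 the first formula reduces to m(1 − rho): 17.2% × 0.75 = 12.9%, × 0.50 = 8.6% and × 0.25 = 4.3% at rho 0.25, 0.50 and 0.75. More generally:

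| | r = 0 | r = 0.25 | r = 0.5 | r = 1 |
|---|---|---|---|---|
| GTC2, rho = 0 | 17.2% | 17.2% | 17.2% | 17.2% |
| GTC2, rho = 0.1 | 15.5% | 16.0% | 16.4% | 17.2% |
| GTC2, rho = 0.3 | 12.0% | 13.5% | 14.9% | 17.2% |
| GTC2, rho = 0.5 | 8.6% | 11.1% | 13.3% | 17.2% |
| GTC1 in the same subjects | 0% | 4.9% | 9.4% | 17.2% |

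Against 17.2% in an unselected GTC1, the planned tables show a false fall whenever rho > 0 and r < 1. Within SP2, GTC2 minus GTC1 equals (m − E)(1 − r)/W. This is positive whenever r < 1 and rho < 1, so a same-subject display shows a false rise.

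**3. Ongoing events.** AEs are placed in a cycle by start date (SAP 11.4.1.2). If every retention event were still open at re-treatment, those subjects would stay in the denominator without adding a new event. Even at rho = 0 the GTC2 rate would be m(1 − m)/W: 16.4% at r = 0.25 and 14.2% at r = 1.

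**4. Trial size.** If every subject could have the event, 15 × 0.172 = 2.6 events are expected in an arm of 15. Zero of 10 in a later cycle has a 95% interval of 0 to 30.8%, and occurs with probability 0.828^10 = 15% at an unchanged 17.2%. In fact few can have it. Protocol 7.4.7 defines a retention AE only for subjects not catheterizing, or with a mixed CIC pattern, at baseline. SAP 8.5.2 puts those voiding spontaneously only, or with an intermittent balloon catheter, at fewer than 5 in total; the mixed-CIC number is not given.

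**5. What GTC1 contains.** SP1 omits placebo subjects who were never re-treated, and placebo-first subjects enter GTC1 only after passing the re-treatment conditions. The total column thus mixes selected and unselected subjects; the split by first treatment separates them. GTC3 holds active-first subjects only.

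**The case against.** The best defence is that the SAP compares nothing across cycles. There are no formal hypotheses, and open-label data receive summary statistics only. The repeated-dose objectives name no comparator, whereas the secondary single-dose efficacy and safety objectives name placebo. That stands: it cannot be said that the objectives call for a cycle-to-cycle comparison. It does not help a reader of the tables, who has no other aggregate view of later doses.

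Second, r = 0 is extreme. The PVR limit applies at least 12 weeks after dosing and does not bar past retention. Protocol 4.6.1 describes the PVR increase as potentially temporary and mainly in the first 12 weeks. A mixed-pattern subject who became CIC-exclusive may no longer fall under the PVR condition as worded. For UTI, past infection is no bar, and no size was calculated. All this stands, and it makes the 4% to 13% range an upper-bound scenario.

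Third, much is already planned: Overall-period AE tables on SP1 (3.45 to 3.52, 3.67, 3.68), follow-up by cycle (Table 1.18), population sizes (Table 1.6), and subject-level listings of special-interest AEs and derived diary data (Listings 22 and 32). With 30 subjects, individuals can be traced. But the Overall tables merge the cycles, Table 1.18 shows unequal follow-up without allowing for it, and listings leave the summary to the reader.

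One might also infer that same-subject columns would settle the matter. Step 2 shows that they reverse the bias for retention. For efficacy, choosing subjects whose incontinence returned in TC1 leaves regression to the mean.

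**Conclusion.** The point holds as one of interpretation and reporting. Later-cycle tables cover selected subjects and active cycles differ in length, both by design, so differences across cycles cannot be put down to repeated dosing. The follow-up and efficacy parts follow from the documents without any assumed rate.

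The retention part is conditional. With unchanged risk, 17.2% could appear in GTC2 as anything from no fall (rho = 0 or r = 1, leaving aside ongoing events) to about 4% to 13% (r = 0, rho from 0.75 to 0.25). A reader might infer that retention is bound to appear to fall with repeated dosing. The documents do not support that: they give neither rho nor r, the 17.2% comes from other studies, and few subjects here can have the event. Chance alone could produce or hide such a pattern. No stated figure in the plan is wrong, and the clinical re-treatment rules are not in question.

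**What to change.** Keep the planned tables and add the following to the SAP:

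1. AE and special-interest AE summaries for the first 84 days after each GSK1358820 injection in GTC1, GTC2 and GTC3, by first-treatment group, extending the window already defined for TC1 (injection date to injection date + 83).
2. For FAS2 and FAS3, Week 6 change in incontinence in TC1 beside TC2 (and TC3) in the same subjects, by first-treatment group.
3. For SP2 and SP3, earlier-cycle AEs beside later-cycle AEs. Add, among subjects who can have the event, counts of those with retention or raised residual urine in the previous cycle who were and were not re-treated.
4. A statement in SAP 7.2 and 8 that changes across cycle tables may reflect selection and follow-up. It should add that neither SP1 against SP2/SP3 nor the same-subject columns alone supports a conclusion on retention with repeated dosing, since the first can show a false fall and the second a false rise.

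The cost is SAP wording and some subset tables from data already collected. The downsides are small subsets and selection that remains, especially in item 2.

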**Day of re-treatment criteria:**

- 1) Patient is asymptomatic for UTI on day of treatment.
- 2) Patient had discontinued any antiplatelet or anticoagulant therapy or medications with anticoagulative effects 3 days prior to re-treatment. Some medications may need to have been withheld for  $> 3$  days per clinical judgment of the investigator (or sub-investigator)
- 3) Negative urine pregnancy test for women of childbearing potential.
- 4) For patients without a UTI as determined from the urinalysis or urine culture using the sample collected at qualification for re-treatment visit and/or investigator opinion, has initiated prophylactic antibiotic medication 1 to 3 days prior to study treatment. For patients with a UTI as determined from the urinalysis or urine culture and/or investigator opinion, has initiated antibiotic medication at least 5 days prior to study treatment.
- 5) No occurrence of bladder stones since entry into the study
- 6) A minimum of 12 weeks (84 days) must have elapsed since the previous treatment
- 7) Period after 1st treatment did not exceed 36 weeks
- 8) Investigator (or sub-investigator) continued to deem a repeat treatment was appropriate and no condition or situation existed which in the investigator's opinion put the patient at significant risk from receiving a repeat treatment

**5.4. Screening Failures**

Screen failures are defined as subjects who consent to participate in the clinical trial but are never subsequently randomized. In order to ensure transparent reporting of screen failure subjects, meet the Consolidated Standards of Reporting Trials (CONSORT) publishing requirements, and respond to queries from Regulatory authorities, a minimal set of screen failure information is required including Demography, Screen Failure details, Eligibility Criteria, and Serious Adverse Events.

**5.5. Withdrawal/Stopping Criteria**

If one of the following events 1) - 6) occurs in a subject, the investigator (or subinvestigator) should withdraw that subject from the study.

- 1) when the subject is lost to follow-up
- 2) when the subject wishes to withdraw from the study

- 3) when it is confirmed that the subject is pregnant
- 4) when the subject is found to meet the liver chemistry stopping criteria (referred to section 5.5.1 Liver Chemistry Stopping Criteria)
- 5) when the subject is found to meet the stopping criteria regarding to QTc (referred to section 5.5.2 QTc Stopping Criteria)
- 6) when the study is prematurely terminated for other reasons not directly related to the study

If one of the following events 7) - 11) occurs in a subject, the investigator (or subinvestigator) may withdraw that subject from the study in his / her judgement.

- 7) when it is difficult to continue the study due to an adverse event(s)
- 8) when a protocol deviation is found
- 9) when it is difficult to continue the study due to exacerbation of the primary disease or a complication
- 10) when subject needs to use prohibited medications / treatments
- 11) when the investigator (or subinvestigator) considers necessary to withdraw the subject from the study for other reasons

The following actions must be taken in relation to a subject who fails to attend the clinic for a required study visit:

[figure not shown]
- The site must attempt to contact the subject and re-schedule the missed visit as soon as possible.
- The site must counsel the subject on the importance of maintaining the assigned visit schedule and ascertain whether or not the subject wishes to and/or should continue in the study.
- In cases where the subject is deemed 'lost to follow up', the investigator or designee must make every effort to regain contact with the subject (where possible, 3 telephone calls and if necessary a certified letter to the subject's last known mailing address or equivalent methods). These contact attempts should be documented in the subject's medical record.
- Should the subject continue to be unreachable, only then will he/she be considered to have withdrawn from the study with a primary reason of "Lost to Follow-up".

A subject may withdraw from study treatment at any time at his/her own request, or may be withdrawn at any time at the discretion of the investigator for safety, behavioural or administrative reasons. If a subject withdraws from the study, he/she may request destruction of any samples taken, and the investigator must document this in the site study records.

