#### 4.1. Overall Design

#### 4.2. Treatment Arms and Duration

This study consists of a Screening phase (within the 28 day-period before first treatment), a Treatment phase 1 (double-blind treatment phase: 12 to 48 week period after first treatment), and a Treatment phase 2 (open-label treatment phase: 12 to 36 week period after first treatment). The duration of overall treatment phase is 48 weeks

Following the Screening phase, patients meeting the eligibility criteria will be randomly assigned by the registration center to one of the 2 treatment arms (either 200 U GSK1358820 or placebo) in a ratio of 1:1. Subsequently, in Treatment phase 1, patients will receive single treatment with the allocated study drug (30 injections each of 1.0 mL) which will be injected into the detrusor of bladder. At the randomization, patients will be stratified according to NDO etiology (spinal cord injury [SCI] with neurological injury level C5 to C8, SCI with neurological injury level T1 or below, or multiple sclerosis[MS]).

Subjects who meet the criteria for re-treatment (referred Re-treatment criteria) between 12 to 36 weeks after 1st treatment can enter to Treatment phase 2 to receive re-treatment (GSK1358820 200 U). Patients are permitted to receive re-treatment up to 36 weeks after 1st treatment and at most 2 times (Note: a minimum of 12 weeks need to be elapsed since the previous study treatment). Subjects who did not receive re-treatment will remain in the Treatment phase 1 and continue to visit at the scheduled study visit. Observation period will be the 48 week period after 1st treatment and patients who complete the evaluation at 48 weeks after 1st treatment are regarded as the patients who complete the study, regardless of whether the subject was re-treated or not.

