7.1.4. Strategy for Intercurrent (Post-Randomization) Events

Following strategy will be planned for intercurrent events. Note that these strategies will be applied for the data until 12 weeks after first administration.

Intercurrent Events	Strategy
Treatment discontinuation / Study withdrawal	Considering the characteristics of study treatment, treatment discontinuation is not defined in this study. In primary analysis, the missing data after study withdrawal will not be imputed and treated as missing. This means it is assumed that missing mechanism is missing-at-random for primary endpoint. This study is not designed to confirm formal statistical hypothesis, so sensitivity analysis will not be done.
Use of protocol inhibited medication	Not planned any specific handling for use of protocol inhibited medication.
Use of rescue medication	Rescue medication is not defined in this study.

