
 The endpoints will be analyzed using an analysis of covariance (ANCOVA) model. Terms fitted in the ANCOVA model will include: 
 Fixed, categorical effects: treatment Fixed, continuous effects: baseline value Since the numbers of subjects of both SCI with neurological injury level C5 to C8 and MS are small, NDO etiology will not be included in MMRM, as described in study protocol. The Kenward-Roger option in SAS PROC MIXED will be used to estimate denominator degrees of freedom and standard errors.
Model Results Presentation

 Adjusted means (LS means) and corresponding SEs of means will be presented for each treatment by visit, together with estimated treatment differences (GSK1358820 – Placebo), the corresponding 95% confidence intervals.

Secondary Statistical Analyses for change from baseline after first treatment
Endpoint(s)

 Change from baseline at week 6 after the first treatment 
 Maximum cystometric capacity (MCC) Maximum detrusor pressure during the first involuntary detrusor contraction (IDC) ($P_{\max IDC}$) Volume at the first involuntary detrusor contraction ($V_{P_{\max IDC}}$) Maximum detrusor pressure during the storage phase ($P_{\det Max}$) KHQ domain score (role limitations, social limitations)
Model Specification

 Same as “Secondary Statistical Analyses for change from baseline after week12 after first treatment”.
Model Results Presentation

 Same as “Secondary Statistical Analyses for change from baseline after week12 after first treatment”.

Secondary Statistical Analyses for Binary data
Endpoint(s)

 Proportion of subjects attaining 100%, $\geq 75\%$ and $\geq 50\%$ reduction from baseline in the daily average of urinary incontinence episodes Proportion of subjects with positive response on the TBS
Results Presentation

 The number and percent of subjects who met each endpoint will be summarized by treatment and visit. The odds ratio and its 95% confidence interval will also be presented.
Missing Data

 Missing data until week 12 after first treatment will be treated as non-responder or no positive response. Missing data after week 12 after first treatment will be treated as missing.

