11. APPENDICES

11.1. Appendix 1: Protocol Deviation Management and Definitions for Per Protocol Population

11.1.1. Exclusions from Per Protocol Population

Per protocol population is not defined in this study.

CONFIDENTIAL

204948

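### Protocol 5.5 lets an investigator end study follow-up, not only further treatment, for any deviation or prohibited therapy, and so loses data the SAP would analyse

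*Protocol*

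**What the plan says.** Protocol 5.5 has two lists. Items 1 to 6 require withdrawal. For items 7 to 11, "the investigator (or subinvestigator) may withdraw that subject from the study in his / her judgement". Item 8 applies "when a protocol deviation is found" and item 10 applies "when subject needs to use prohibited medications / treatments". Neither is limited by importance, safety relevance or timing, and in both the subject leaves the study, not only study treatment. Item 11 is a general clause for other reasons. The closing paragraph of 5.5 adds a broad discretion that extends to administrative grounds.

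Protocol 4.2 gives one session of 30 injections in Treatment phase 1, with up to two open-label re-treatments from Week 12.

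SAP 7.1.4 says "treatment discontinuation is not defined in this study" and, on prohibited therapy, "Not planned any specific handling for use of protocol inhibited medication". SAP 11.1.1 says "Per protocol population is not defined in this study". For the primary endpoint, values after study withdrawal are left missing under a missing-at-random assumption, and no sensitivity analysis is planned. For the incontinence-responder and TBS proportions, SAP 7.2.5.1 says "Missing data until week 12 after first treatment will be treated as non-responder or no positive response" (the DO=NR rule); missing data after Week 12 stay missing.

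**The concern.** In the double-blind cycle there is no continuing treatment to stop. Withdrawing a subject under item 8 or 10 therefore does little except end the assessments and the route to re-treatment. Had the subject stayed, the SAP would have analysed the later diaries and questionnaires as collected. Because the rule is discretionary, two subjects with the same event can have observed data in one case and none in the other.

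The losses could be related to outcome or arm. Protocol 6.9.1 requires a stable dose of incontinence medication through Treatment phase 1, so raising it for lack of effect is a deviation. Protocol 6.9.2 restricts indwelling catheters, intravesical agents and, for 8 weeks after treatment, aminoglycosides. Protocol 4.6.1 reports urinary retention in 17.2% on 200 U against 2.9% on placebo, and urinary tract infection in 49.2% against 35.7%. Triggers could thus come from inefficacy in one arm and drug effect in the other. With 30 subjects and no formal test, the estimates are the evidence, and a few lost subjects are visible in them.

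**Working it through.** **Plan's own figures.** Inputs from Protocol 9.2.1: 15 per arm, difference -1.5, common SD 3.0 episodes/day, two-sided 5%.

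- Standard error = 3.0 × √(2/15) = 1.095.
- Two-sample t-test power (28 df) = 26.2%; the plan states 26%.
- Probability that the estimate favours active = Φ(1.5/1.095) = 91.5%; the plan states about 92%.
- Unadjusted 95% CI half-width = 2.24 episodes/day.

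Both stated figures reproduce.

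**Which visits are lost.** The Time and Events Table schedules a withdrawal visit with diary, King's Health Questionnaire and TBS. SAP 11.7.1 allows it to be slotted into the efficacy windows of SAP 11.3.1, and SAP 11.6.3 accepts one valid diary day.

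| Window holding the withdrawal data | Primary Week 6 value | Scored as non-response |
|---|---|---|
| Day 2–29 (Week 2) | lost | Weeks 6 and 12 |
| Day 30–64 (Week 6) | available | Week 12 |
| Day 65–106 (Week 12) | available if Week 6 was attended | none |

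The diary excludes the visit day (Protocol 7.3.1.1), and a diary that starts before a window does not count in it (SAP 11.6.3, example 1). A full three-day diary starting on Day 30 therefore belongs to a visit on Day 30 + 3 = Day 33 or later. So the primary value is mainly at risk from withdrawal in roughly the first month. Urodynamic testing is not scheduled at withdrawal, so leaving before Week 6 can also lose those endpoints. A subject with no post-baseline efficacy assessment leaves FAS1 (SAP 4) and is not scored at all.

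**Responder and TBS tables.** Assume 15 per arm in FAS1.

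- Each responder withdrawn and scored as non-response: 1/15 = 6.7 points. Two: 2/15 = 13.3 points.
- Illustration with assumed rates 10/15 and 5/15: odds ratio = (10/5)/(5/10) = 4.00.
- One active responder lost: (9/6)/(5/10) = 3.00. Two: (8/7)/(5/10) = 2.29.
- One placebo responder lost instead: (10/5)/(4/11) = 5.50.

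**Primary endpoint.** Let k subjects in one arm lose Week 6, each with a true change D away from what the model predicts. The arm mean shifts by k × D/15. Both k and D are assumptions.

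- k = 1, D = 1.5: 0.10 episodes/day, or 0.10/1.5 = 6.7% of the assumed effect.
- k = 2, D = 3.0: 0.40 episodes/day, or 0.40/1.5 = 26.7%.
- Against the half-width of 2.24, these are 0.10/2.24 = 4.5% and 0.40/2.24 = 17.9%.

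**Precision.** Losing one Week 6 value per arm (14 against 14) gives power 24.7%, direction probability 90.7% and half-width 2.33. Losing three per arm gives 21.6%, 89.0% and 2.54.

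**The case against.** The strongest reply is that the plan already limits the damage. The withdrawal visit can supply the Week 6 or Week 12 value. Data collected before withdrawal stay in FAS1 and in the model. Treatment phase 1 is double-blind. Important deviations and withdrawal reasons are summarised or listed. Withdrawal is optional, its frequency is unknown, and several prohibited therapies have no evident link to efficacy. All of this stands, and it reduces the point from a serious bias to a cheap improvement.

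Three stronger readings are tempting, and the documents do not support them.

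- A reader might infer that the two documents contradict each other. They do not. SAP 7.1.4 expects study withdrawals and states how to handle them. The issue is a design choice that loses usable data.
- A reader might call the rule a per-protocol exclusion run by the sites. It removes later visits. It does not remove a subject who already has a post-baseline efficacy assessment.
- A reader might infer that a withdrawn subject counts as a failure throughout. The primary endpoint has no failure scoring, and SAP 7.2.5.1 stops it at Week 12 for the binary endpoints.

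Withdrawal also does more than stop data collection, since it ends access to re-treatment. Deleting items 8 and 10 alone would not work either, because item 11 and the closing paragraph of 5.5 leave the same route open.

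**Conclusion.** The point holds for the double-blind comparison to Week 12. Protocol 5.5 allows follow-up to end for events after which the SAP would still use the data. The loss is then handled by an untested missing-at-random assumption in the primary model, and by non-response scoring of unfilled visits to Week 12 in the responder and TBS tables.

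Each responder so lost costs an arm 6.7 points, assuming 15 per arm in FAS1. The possible shift of 0.10 to 0.40 episodes/day in a primary arm mean rests on an assumed one or two subjects and an assumed departure of 0.5 to 1 SD, and is small against the 2.24 half-width. The net direction cannot be predicted from the documents. The existing discretion need not produce any withdrawals. This is a cheap improvement, not a flaw that undermines the trial.

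**What to change.** In Protocol 5.5, state that a protocol deviation or use of a prohibited therapy is not in itself a reason to end study follow-up. Unless consent is withdrawn or the subject is lost to follow-up, such a subject continues the scheduled diary, questionnaire, urodynamic and safety assessments at least to Week 12, with the event recorded. Reword item 11 and the administrative-grounds wording in the closing paragraph so that they do not reopen the same route.

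The change concerns follow-up only. Decisions on further study treatment stay with the investigator under 5.3, and withdrawal under items 7 and 9 is unchanged.

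The cost is a wording amendment in one section, since the visits are already scheduled. The downside is that some diaries kept under a prohibited therapy enter the analysis, which SAP 7.1.4 already accepts.

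One related SAP edit is needed. The TBS derivation in SAP 11.6.3 scores missing answers as no positive response without a week limit, whereas SAP 7.2.5.1 stops at Week 12. The two should be reconciled.
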